****If the forehead has perspiration present, measure the temperature from behind the ear instead.***

1. Instead of placing probe on center of forehead, place it on the neck just behind the ear lobe.
2. Press and hold grey button as before and take a reading while keeping the probe stationary in that spot.

Pulse Oximeter Protocol

1. Remove blue Pulse Oximeter (pulse-ox) from blue carrying case.
2. Squeeze the end of the pulse-ox that says PUSH to open the clip.
3. Place the child's index or thumb into the clip and release the pulse-ox so it gently squeezes the finger.
 - a. The child's fingernail should be facing up, toward the display. Don't put the pulse-ox on upside down!
 - b. Make sure the child is not moving and is at ease during this process.
4. Press the white button on the top and it will turn on and start to take a reading.
 - a. You'll notice red LED lights show up on the display.
 - b. The reading will take a few seconds before it shows up on the display.
 - c. Once it's ready, you will see two numbers:
 - i. The first number will appear about "PRbpm," which is your current Heart Rate
 - ii. The second number appears above "%SpO2," which is your oxygen percentage.
 - d. Wait at least 10 seconds after the first reading shows up before you record the numbers.
 - e. Write the two measurements down on the [Health Measures Visit Sheet](#).
5. Gently press the PUSH end of the pulse-ox again to open the clip and release the finger.
6. The pulse-ox will turn off on its own.
7. Use an alcohol swab to gently clean the inside of the clip.
8. You can store it back in its blue carrying case.
9. If the low battery icon shows up on the display, you need to switch out the batteries.
 - a. Flip the pulse-ox over and slide off the blue battery cover.
 - b. Replace the two AAA batteries.
 - c. Replace the blue cover.

Referral Protocol

The outcomes targeted in the KidsAIR study are illnesses in children so it is anticipated that significant illness might be encountered. Epidemiologic data and other studies give evidence that such cases are few but ethically plans should be in place for field workers encountering them (RESPIRE studies, RSV statistics). In keeping with the Presidential Commission for the Study of Bioethical Issues (Bioethics Commission) in its report, *Anticipate and Communicate: Ethical Management of Incidental and Secondary Findings in the Clinical, Research, and Direct-to-Consumer Contexts* (http://bioethics.gov/sites/default/files/FINALAnticipateCommunicate_PCSBI_0.pdf), the following outline describes our protocol for management of incidental illnesses in the subjects enrolled in the KidsAIR study.

1. The medical resources of specific areas will be determined by participating investigators prior to collection of any field data and that list of resources will be provided to each field worker in anticipation of emergent or urgent needs. That list will include local Emergency Medical Services, physicians and health care facilities. In some specific areas, families are served by health care aides or nurses and when that is the case those persons will be the first contact for non-emergent cases.
2. Local healthcare providers will be contacted prior to study initiation and made aware of the nature of the study and intent of the fieldworkers.
3. Educational sessions will be provided to each field worker outlining signs of serious illness for the age groups being studied (World Health Organization – IMCI program). Signs of illness will be categorized as life threatening (emergent), urgent, or recommended for scheduled evaluation by a health care provider. Each category of illness will initiate a different level of response.
 - a. Emergency calls will be made to the closest available emergency personnel. The field workers will stay at the home until emergency personnel arrive.
 - b. Urgent calls (non-emergency but needing care in less than 24 hours) will be made to the primary health care provider identified by the parents. Should the family have no such provider, the closest emergency room and health care provider will be contacted.
 - c. For illnesses that do not require emergent or urgent care, the parents will be advised to contact their health care provider. The field data collector will volunteer to help families make contact with appropriate health care providers. A phone call to the family will be made the following day to ensure referral has been made.
4. The field worker will first discuss concerns for incidental findings with the parent or care provider and they will be asked if they have a health care provider. If time allows, that person or facility will be the first notified of possible need for medical care. If the child does not have a primary care provider, a list of possible medical care providers or institutions will be provided.

Referral Protocol (continued)

Emergent signs and symptoms - call for immediate assistance to 911 local EMS

- Not breathing
- Cyanosis (blue coloration to the skin)
- Unresponsive to stimulation
- Pulseless or thread, weak pulse
- Seizures

Urgent care (call to local health care aid or physician)

- Difficulty breathing – retractions involving use of neck muscles and lower chest
- Pulse oximetry less than 90%
- Respiratory Distress – wheezing, stridor, muffled voice, difficulty speaking
- Coughing up blood
- Listlessness
- Fever > 100.4 °F (<2 month)
 - > 102.2 °F (2 months – 12 months)
 - > 102.2 °F and ill appearing (>12 months)
- Active bleeding
- Stiff neck and signs of mental status change or fever

Recommend follow up with primary care provider within the next day

- Wheezing not responsive to home medications but little or no distress
- Prolonged fever (more than 2 days)
- Prolonged cough (> 3 days)
- Prolonged illness and not getting better (>1 week)

HOME CHARACTERISTICS DATA SHEET

Technician: _____ Home ID: _____ Winter (1,2,3,etc.): _____

Sampling Dates: _____ Date form completed: _____

To be completed by an adult resident once at the beginning of each winter.

1. Number of total residents in home: _____
2. Number of residents younger than 18 years of age: _____
3. Number of residents younger than 5 years of age: _____
4. Type of home: House Mobile Home Duplex/Apt Other: _____
5. Year home built: _____
6. Square footage of home: _____
7. Number of floors (not incl. bsmnt): 1 2 3
8. Number of windows: _____
9. Number of bedrooms: _____
10. Total number of pets: _____
11. Total number of "furry" pets: _____
12. Type of primary heating (Please circle **ONLY** one choice that represents your most common practice):
Wood stove Electrical Propane Natural gas furnace Oil Other: _____
13. Type of secondary heating (Please circle **ONLY** one choice that represents your most common practice):
Wood stove Electrical Propane Natural gas furnace Oil Other: _____
14. Existing appliance(s): Fireplace Wood stove Furnace Wood stove insert
15. Wood stove model (*If you have access, information is located on the back of the stove*):

16. Approximately how old is your wood stove:
0-5 years old 6-10 years old 11-15 years old 16 + years old

17. Is your wood stove EPA-certified? Yes No I don't know

18. When was the last time you had your chimney cleaned?

Less than 6 months ago 6-12 months ago 12-18 months ago more than 18 months ago

19. Within the last 12 months have you had wet or damp spots on surfaces inside your home other than in the basement (for example on walls, wall paper, ceilings or carpets)?

Yes No I don't know

20. Has there been mold or mildew on any surfaces inside your home in the last 12 months?

Yes No I don't know

HOME ACTIVITY LOG

Technician:

Home ID:

Winter (1,2,3,etc.):

Sampling Day (1 – 6):

Sampling Date:

To be completed by an adult resident for each day of six day sampling visit.

1. Were any of the following heating appliances, other than your woodstove, used in the home during the sampling period?

- | | | |
|-------------------------|----|-----|
| • Gas | No | Yes |
| • Electrical | No | Yes |
| • Propane | No | Yes |
| • Oil | No | Yes |
| • Other, specify: _____ | No | Yes |

2. Did any of the following activities or conditions occur in the home during the sampling period?

- | | | |
|---|----|-----|
| • Smoking by anyone in the home (cigarette, pipe, or other) | No | Yes |
| • Incense burning | No | Yes |
| • Candle burning | No | Yes |
| • Kerosene/oil lamp | No | Yes |
| • Open windows | No | Yes |
| • Front door propped open | No | Yes |
| • Dusting/sweeping/vacuuming | No | Yes |

Revised October 6, 2014

WOOD STOVE USAGE LOG

Technician:

Home ID:

Winter (1,2,3,etc.):

Sampling Dates:

Date form completed:

To be completed by an adult resident at the end of each six day sampling visit.

1. During the sampling period, how would you describe the level of wood burning compared to a typical winter day (circle one):

No burning Light burning Average burning Heavy burning

2. What kind of wood was used or was used most frequently? *Please choose **ONLY** one.*

Lodgepole Pine Ponderosa Pine Fir Larch

[LIST OTHER COMMON TYPES] _____

3. When do you get your wood before burning? (Please circle **ONLY** one choice that represents your most common practice)

A few days Between 1 week and 1 month

Between 1 month and 3 months Between 3 months and 6 months

Between 6 months and 1 year More than 1 year

4. On average, how many cords of wood do you burn each year? _____ cords

5. How do you usually acquire your wood? (Please circle **ONLY** one choice that represents your most common practice)

Harvest yourself Purchase it Other: _____

IN HOME LOG

Technician:

Home ID:

Child ID:

Winter:

Sampling dates:

Sampling start time:

To be completed by an adult resident for each participating child for each 24 hour period of six day sampling visit.

For each row, please mark the day of week (M, T, W, Th, F, Sa, Su) and whether your child was or was not home. If your child was not at home, please mark the circle indicating where your child was.

Age of participating child: _____

Child is a: girl boy

Day	Day of week	Time			At home?		If not home, where?				
							school	day care	relative's house	friend's house	other
1		7:00 AM	to	8:00 AM	Y	N					
1		8:00 AM	to	9:00 AM	Y	N					
1		9:00 AM	to	10:00 AM	Y	N					
1		10:00 AM	to	11:00 AM	Y	N					
1		11:00 AM	to	12:00 PM	Y	N					
1		12:00 PM	to	1:00 PM	Y	N					
1		1:00 PM	to	2:00 PM	Y	N					
1		2:00 PM	to	3:00 PM	Y	N					
1		3:00 PM	to	4:00 PM	Y	N					
1		4:00 PM	to	5:00 PM	Y	N					
1		5:00 PM	to	6:00 PM	Y	N					
1		6:00 PM	to	7:00 PM	Y	N					
1		7:00 PM	to	8:00 PM	Y	N					
1		8:00 PM	to	9:00 PM	Y	N					
1		9:00 PM	to	10:00 PM	Y	N					
1		10:00 PM	to	7:00 AM	Y	N					

Home ID:

Child ID:

Winter:

Sampling dates:

Sampling start time:

Day	Day of week	Time			At home?		If not home, where?				
							school	day care	relative's house	friend's house	other
2		7:00 AM	to	8:00 AM	Y	N					
2		8:00 AM	to	9:00 AM	Y	N					
2		9:00 AM	to	10:00 AM	Y	N					
2		10:00 AM	to	11:00 AM	Y	N					
2		11:00 AM	to	12:00 PM	Y	N					
2		12:00 PM	to	1:00 PM	Y	N					
2		1:00 PM	to	2:00 PM	Y	N					
2		2:00 PM	to	3:00 PM	Y	N					
2		3:00 PM	to	4:00 PM	Y	N					
2		4:00 PM	to	5:00 PM	Y	N					
2		5:00 PM	to	6:00 PM	Y	N					
2		6:00 PM	to	7:00 PM	Y	N					
2		7:00 PM	to	8:00 PM	Y	N					
2		8:00 PM	to	9:00 PM	Y	N					
2		9:00 PM	to	10:00 PM	Y	N					
2		10:00 PM	to	7:00 AM	Y	N					
3		7:00 AM	to	8:00 AM	Y	N					
3		8:00 AM	to	9:00 AM	Y	N					
3		9:00 AM	to	10:00 AM	Y	N					
3		10:00 AM	to	11:00 AM	Y	N					
3		11:00 AM	to	12:00 PM	Y	N					
3		12:00 PM	to	1:00 PM	Y	N					
3		1:00 PM	to	2:00 PM	Y	N					
3		2:00 PM	to	3:00 PM	Y	N					
3		3:00 PM	to	4:00 PM	Y	N					
3		4:00 PM	to	5:00 PM	Y	N					
3		5:00 PM	to	6:00 PM	Y	N					
3		6:00 PM	to	7:00 PM	Y	N					
3		7:00 PM	to	8:00 PM	Y	N					
3		8:00 PM	to	9:00 PM	Y	N					
3		9:00 PM	to	10:00 PM	Y	N					
3		10:00 PM	to	7:00 AM	Y	N					

Home ID:
 Child ID:
 Winter:
 Sampling dates:
 Sampling start time:

Day	Day of week	Time			At home?		If not home, where?				
							school	day care	relative's house	friend's house	other
4		7:00 AM	to	8:00 AM	Y	N					
4		8:00 AM	to	9:00 AM	Y	N					
4		9:00 AM	to	10:00 AM	Y	N					
4		10:00 AM	to	11:00 AM	Y	N					
4		11:00 AM	to	12:00 PM	Y	N					
4		12:00 PM	to	1:00 PM	Y	N					
4		1:00 PM	to	2:00 PM	Y	N					
4		2:00 PM	to	3:00 PM	Y	N					
4		3:00 PM	to	4:00 PM	Y	N					
4		4:00 PM	to	5:00 PM	Y	N					
4		5:00 PM	to	6:00 PM	Y	N					
4		6:00 PM	to	7:00 PM	Y	N					
4		7:00 PM	to	8:00 PM	Y	N					
4		8:00 PM	to	9:00 PM	Y	N					
4		9:00 PM	to	10:00 PM	Y	N					
4		10:00 PM	to	7:00 AM	Y	N					
5		7:00 AM	to	8:00 AM	Y	N					
5		8:00 AM	to	9:00 AM	Y	N					
5		9:00 AM	to	10:00 AM	Y	N					
5		10:00 AM	to	11:00 AM	Y	N					
5		11:00 AM	to	12:00 PM	Y	N					
5		12:00 PM	to	1:00 PM	Y	N					
5		1:00 PM	to	2:00 PM	Y	N					
5		2:00 PM	to	3:00 PM	Y	N					
5		3:00 PM	to	4:00 PM	Y	N					
5		4:00 PM	to	5:00 PM	Y	N					
5		5:00 PM	to	6:00 PM	Y	N					
5		6:00 PM	to	7:00 PM	Y	N					
5		7:00 PM	to	8:00 PM	Y	N					
5		8:00 PM	to	9:00 PM	Y	N					
5		9:00 PM	to	10:00 PM	Y	N					
5		10:00 PM	to	7:00 AM	Y	N					

Home ID:
 Child ID:
 Winter:
 Sampling dates:
 Sampling start time:

Day	Day of week	Time		At home?		If not home, where?					
						school	day care	relative's house	friend's house	other	
6		7:00 AM	to	8:00 AM	Y	N					
6		8:00 AM	to	9:00 AM	Y	N					
6		9:00 AM	to	10:00 AM	Y	N					
6		10:00 AM	to	11:00 AM	Y	N					
6		11:00 AM	to	12:00 PM	Y	N					
6		12:00 PM	to	1:00 PM	Y	N					
6		1:00 PM	to	2:00 PM	Y	N					
6		2:00 PM	to	3:00 PM	Y	N					
6		3:00 PM	to	4:00 PM	Y	N					
6		4:00 PM	to	5:00 PM	Y	N					
6		5:00 PM	to	6:00 PM	Y	N					
6		6:00 PM	to	7:00 PM	Y	N					
6		7:00 PM	to	8:00 PM	Y	N					
6		8:00 PM	to	9:00 PM	Y	N					
6		9:00 PM	to	10:00 PM	Y	N					
6		10:00 PM	to	7:00 AM	Y	N					
7		7:00 AM	to	8:00 AM	Y	N					
7		8:00 AM	to	9:00 AM	Y	N					
7		9:00 AM	to	10:00 AM	Y	N					
7		10:00 AM	to	11:00 AM	Y	N					
7		11:00 AM	to	12:00 PM	Y	N					
7		12:00 PM	to	1:00 PM	Y	N					
7		1:00 PM	to	2:00 PM	Y	N					
7		2:00 PM	to	3:00 PM	Y	N					
7		3:00 PM	to	4:00 PM	Y	N					
7		4:00 PM	to	5:00 PM	Y	N					
7		5:00 PM	to	6:00 PM	Y	N					
7		6:00 PM	to	7:00 PM	Y	N					
7		7:00 PM	to	8:00 PM	Y	N					

End of Winter Questionnaires

Education Homes:

1. Post winter Questionnaire Education Homes
2. KAB Education Homes Post Winter 1 & 2 Assessment

Filter Homes:

1. Post winter Questionnaire Filter Homes
2. KAB Filter Homes Post Winter 2 Assessment

Post Winter Questionnaire - Education Homes

Home ID: _____

Technician: _____

Date: _____

Filled out by: Mother Father Other: _____

Please complete the following brief survey regarding your experiences this winter. Please circle your response below each item.

1. How often did you use the moisture meter during this winter?

Never Once Once a Month Weekly Daily

2. Did you split the wood and take the reading from the freshly cut portion of the log?

Yes No Not Applicable

3. How easy has it been to use the moisture meter?

Difficult Somewhat Difficult Somewhat Easy Easy Not Applicable

4. Has the moisture meter been helpful to you this winter?

Not Helpful Not Very Helpful Somewhat Helpful Very Helpful

If it was not helpful, can you tell us why?

5. How often did you use the wood stove thermometer during this winter?

Never Once Once a Month Weekly Daily

6. How easy has it been to use the wood stove thermometer?

Difficult Somewhat Difficult Somewhat Easy Easy Not Applicable

7. Has the wood stove thermometer been helpful to you this winter?

Not Helpful Not Very Helpful Somewhat Helpful Very Helpful

If it was not helpful, can you tell us why?

8. How often did you use the firestarters during this winter?

Never Once Once a Month Weekly Daily

9. How easy has it been to use the firestarters?

Difficult Somewhat Difficult Somewhat Easy Easy Not Applicable

10. Have the firestarters been helpful to you this winter?

Not Helpful Not Very Helpful Somewhat Helpful Very Helpful

If it was not helpful, can you tell us why?

11. How often did you recall or watch the educational videos during this winter?

Never Once Once each Month Weekly

12. How easy has it been to use the guidelines included in the educational videos?

Difficult Somewhat Difficult Somewhat Easy Easy Not Applicable

13. Have the guidelines included in the educational videos been helpful to you this winter?

Not Helpful Not Very Helpful Somewhat Helpful Very Helpful

If it was not helpful, can you tell us why?

14. Our staff called you at least once a month throughout the study to check in on your child's health and to ask a few questions about your wood stove. Were these phone calls helpful with troubleshooting issues regarding your wood stove?

Not Helpful Not Very Helpful Somewhat Helpful Very Helpful

If these calls were not helpful, can you tell us why?

15. Was there anything new/interesting/helpful that you learned this winter about burning more efficiently and/or cleaner with your wood stove?

KAB - Education Homes - Post Winter 1 & 2 Assessment

Home ID: _____

Date: _____

Filled out by: Mother

Father

Other: _____

The following questions will help us learn more about your woodstove use habits and behaviors. There are no “right or wrong” answers to these items. This information will help us understand how useful the educational materials and videos were for you this winter. Please rank the following items in terms of how important, helpful, and useful the following suggestions were when you used your wood stove the past winter.

Please rank the items on a scale of 1-4

(1 = not important at all, 2= not very important, 3 = somewhat important, 4 = very important)

During the past year how important has it been:

- To split your firewood in smaller sizes (6 inches or less in diameter)? _____
- To store your firewood in a covered wood pile? _____
- To season firewood for 6-12 months before burning? _____
- To use a moisture meter to test your wood? _____
- To only burn dry, seasoned wood (moisture content <20%)? _____
- To maintain a bed of ash just below the vent holes of the wood stove? _____
- To crack a window/door on the same level when starting a fire? _____
- To use dry kindling, air movement, and fire starters to help you start a hot fire? _____
- To allow small hot fires that burn for 20 to 30 minutes to reach optimal burn temperatures? _____
- To use a wood stove thermometer to help you burn at specific desired temperatures _____
- To check your wood stack 20-30 minutes after starting to burn? _____
- To allow the fire to burn for 20-30 minutes before refueling? _____
- To not burn items other than wood (e.g., trash, cardboard, etc.)? _____
- To clean your flue and chimney? _____
- To condition or dry wood inside for 2 days before burning? _____
- To determine wood stove model and locate manual _____

Post Winter Questionnaire - Filter Homes

Home ID: _____

Technician: _____

Date: _____

Filled out by: Mother Father Other: _____

Please complete the following brief survey regarding your experiences this winter. Please circle your response below each item.

1. Did you use your Filter unit this winter? Yes No
2. Did you use your Filter unit continuously throughout the winter? Yes No
3. If you did not use your Filter unit continuously, approximately how many hours per week did you have your Filter unit turned on? _____
4. On what setting(s) did you use your Filter unit when you had it turned on? Please indicate the percentage of time on each setting below:

High _____ Medium _____ Low _____

5. If you decided not to use the Filter unit, what were the reasons?

Noise Cost Appearance Space Concerns Inconvenience N/A

Other _____

Other _____

6. Of the reasons above, which was the most important reason?

_____ N/A

7. Overall, do you think the Filter unit has been helpful to you and/or your family this winter?

Not Helpful Not Very Helpful Somewhat Helpful Very Helpful

KAB - Filter Homes - Post Winter 2 Assessment

Home ID: _____

Date: _____

Filled out by: Mother

Father

Other: _____

The following questions will help us learn more about your woodstove use habits and behaviors. There are no “right or wrong” answers to these items. This information just helps us understand your woodstove usage. Please rank the following items in terms of how important these factors are when you have used your wood stove the past two years.

Please rank the items on a scale of 1-4

(1 = not important at all, 2= not very important, 3 = somewhat important, 4 = very important)

During the past two years how important has it been:

- To split your firewood in smaller sizes (6 inches or less in diameter)? _____
- To store your firewood in a covered wood pile? _____
- To season firewood for 6-12 months before burning? _____
- To use a moisture meter to test your wood? _____
- To only burn dry, seasoned wood (moisture content <20%)? _____
- To maintain a bed of ash just below the vent holes of the wood stove? _____
- To crack a window/door on the same level when starting a fire? _____
- To use dry kindling, air movement, and fire starters to help you start a hot fire? _____
- To allow small hot fires that burn for 20 to 30 minutes to reach optimal burn temperatures? _____
- To use a wood stove thermometer to help you burn at specific temperatures? _____
- To check your wood stack 20-30 minutes after starting to burn? _____
- To allow the fire to burn for 20-30 minutes before refueling? _____
- To not burn items other than wood (e.g., trash, cardboard, etc.)? _____
- To clean your flue and chimney? _____
- To condition or dry wood inside for 2 days before burning? _____
- To determine wood stove model and locate manual? _____

Statistical Analysis Plan

Analysis was conducted using R version 3.6.2 (The R Foundation for Statistical Computing, Austria). We calculated descriptive statistics for continuous variables (n, mean, standard deviation [sd], minimum [min], median, maximum [max]) and categorical variables (n, percentage of total) across all study households and separately for each treatment arm and study area. We averaged indoor concentrations of PM_{2.5} over the 6-day sampling period for each home and for the times during which each child was reported as being at the household.

Primary analyses were conducted within three model frameworks using the lme4 package (Bates et al. 2015): 1) intent-to-treat (ITT) framework with LRTI outcome (ITT-LRTI), 2) ITT framework with PM_{2.5} outcome (ITT-PM_{2.5}), and 3) exposure-response (ER) framework with LRTI as the outcome and PM_{2.5} as the exposure of interest. Although LRTI cases were collected as count data, very few children had more than one LRTI, resulting in under-dispersed data that violated the assumptions of attempted Poisson and negative binomial regression models. Thus, the ITT-LRTI framework utilized mixed effects logistic regression models (using the glmer function) with presence of LRTI (yes or no) as the outcome and assigned treatment as the exposure of interest. The ITT-LRTI models included a covariate for person-time at risk to account for the wide variability of child-weeks at risk across study participants. The models also included a covariate for child age (<1 year vs. 1 to 4 years) since randomization occurred within strata of this term. A nested random term (i.e., household:cohort:area) was included in the model to account for repeated measures clustered within household, cohort, and study area. The ITT-PM_{2.5} framework used mixed effects linear models (using the lmer function) with mean 6-day indoor PM_{2.5} concentration as the outcome and assigned treatment as the exposure of interest. Models were adjusted for child age and included a nested random term of cohort:area (there were no repeated measures within household for PM_{2.5}). Both ITT models utilized the study's randomization and were not adjusted for potential confounding variables in the primary analyses.

The ER framework utilized mixed effects logistic regression models (using the glmer function) with presence of LRTI (yes or no) as the outcome and mean 6-day indoor PM_{2.5} concentration as the exposure of interest. As with the ITT-LRTI models, ER models were adjusted for person-time at risk and included a nested random term (i.e., household:cohort:area) to account for repeated measures in the analysis. In addition, since the ER models did not utilize the study's randomization to help control for confounding, covariates were included in the model to adjust for potential confounders. Confounders were identified a priori through previous literature and by assessing independent associations with the exposure and outcomes of interest (Adaji et al. 2019; Mortimer et al. 2017; [name] et al. 2019; Smith et al. 2011; Walker et al. 2021). We also used directed acyclic graphs (DAGs) to assess the direction and potential relationship between indoor PM_{2.5}, LRTI, and covariates (Figure S3). Final ER models were adjusted for child age and sex, caregiver race and sex, household income, caregiver education, if a household resident smoked, and ambient temperature and PM_{2.5}.

The primary ITT model framework was prespecified in our previously published methods paper ([name] et al. 2019). We conducted a number of sensitivity analyses in all model frameworks that were specified a priori (during the initial model development when the analyst was masked to treatment arm assignment) and assessed the impact of including potential confounders in the models and using subsets of the data. We conducted sensitivity analyses by including potential confounders that had some imbalance across study arms (ITT frameworks) or by including additional potential confounders not included in the primary model (ER framework). Due to the different control treatment in AK (no filtration unit), we conducted the ITT-LRTI and ITT-PM_{2.5} analyses with AK households excluded from the dataset. For the ITT-LRTI and ER frameworks, we also conducted a sensitivity analysis with a dataset restricted to Winter 1 only, as this was the only winter of observation when indoor PM_{2.5} was sampled. For the ER framework we conducted an additional sensitivity analysis that used indoor PM_{2.5} when each child was at home as the primary exposure variable in place of indoor PM_{2.5} over the entire sampling period.

We also conducted some post hoc sensitivity analyses for the ITT-LRTI framework with other model variations to provide insight into our primary model selection and results. Specifically, we assessed models that 1) used

study area (AK, NN, WMT) as a fixed effect rather than a random nested term, 2) removed the covariate for person-time at risk, and 3) removed the random nested term for household.

We evaluated potential modification of the effect of the treatments by a priori selected child, caregiver, and home characteristics within each of the model frameworks by including interaction terms in the primary model. We assessed significance of the interaction terms using Type II Wald Chi-square tests. Model assumptions were evaluated in all analysis frameworks. Indoor PM_{2.5} concentrations were natural-log transformed in the ITT-PM_{2.5} framework, and estimates are presented as percent difference in geometric mean PM_{2.5}.

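### The primary exposure-response model has no fixed term for study area, and no fixed-area check is stated for it, so differences between areas can enter the PM2.5 estimate

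*Combined protocol and SAP*

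**What the plan says.** The Statistical Analysis Plan names three primary frameworks: ITT with LRTI, ITT with PM2.5, and ER. The ER model is a mixed logistic regression of LRTI (yes/no) with "mean 6-day indoor PM_{2.5} concentration as the exposure of interest". The SAP says covariates are needed here "since the ER models did not utilize the study's randomization to help control for confounding". The list reads: "Final ER models were adjusted for child age and sex, caregiver race and sex, household income, caregiver education, if a household resident smoked", and ends with ambient temperature and ambient PM2.5. Person-time at risk is also in the model.

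Study area is not among these fixed terms. The model "included a nested random term (i.e., household:cohort:area) to account for repeated measures in the analysis". For the ITT-LRTI model the SAP gives the purpose of the same term as "to account for repeated measures clustered within household, cohort, and study area".

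The stated sensitivity analyses divide as follows:

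- Area as a fixed effect: post hoc, for ITT-LRTI only.
- Alaska excluded: for the two ITT frameworks only.
- ER: first winter only; PM2.5 restricted to the hours the child was at home; and extra potential confounders, which are not named.

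**The concern.** In the ITT models area is a weak threat. The project summary plans 108 homes per area, split equally over three arms (108 / 3 = 36 per arm), so area is balanced across arms by design. The ER exposure is measured, not assigned, and nothing balances it across areas. The fixed-area check is therefore stated for the model that needs it less, and not for the one that needs it more.

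Area differences are plausible from the documents. The three settings are distinct, and protocol item 7.3 says that some activities affecting exposure are particular to a site. Item 7.3 also says that communication barriers may vary by community. It answers this with active surveillance and a measured case definition, so area-linked case ascertainment is only a possibility.

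If areas differ in both indoor PM2.5 and recorded LRTI, the coefficient can show an association that exists in no area, or shrink one that exists in all of them.

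**Working it through.** **1. What the random term does.** Write the model as logit P(LRTI) = β·PM2.5 + γ′Z + α(area) + u(household), where Z holds the listed covariates. If α(area) is left out and is correlated with PM2.5 given Z, the estimate of β is a mixture of the within-area and between-area slopes. The SAP's term can be read in two ways:

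- Literally, in lme4 syntax, `household:cohort:area` is one grouping factor. That gives a household intercept and no area intercept, so α(area) is left out.
- Elsewhere the SAP speaks of clustering in each of the three levels, and of area and household as random nested terms. That suggests a separate area intercept, which absorbs most of α(area).

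**2. Whether the covariates stand in for area.** They do in part. The caregiver form has a single American Indian/Alaskan Native category, which separates Navajo Nation from Alaska poorly. Ambient temperature may separate them, but less well the more it varies within an area.

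**3. Mechanism, without covariates.** An illustrative simulation used 3 areas × 108 homes, 3 records per home, within-area exposure SD 0.8, household SD 0.6, a true OR of 1 and 60 runs. ORs are per unit of simulated exposure.

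| Area shift in exposure; in log-odds | Household-only | Plus area intercept | Area fixed |
|---|---|---|---|
| 0; ±0.8 | 1.02 | 1.02 | 1.02 |
| ±0.3; ±0.4 | 1.13 | 1.03 | 1.01 |
| ±0.6; ±0.8 | 1.46 | 1.01 | 1.00 |

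This shows the direction only. It overstates the size, because the SAP's covariates are absent.

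**4. Size, with all listed covariates and untransformed PM2.5.**

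From the documents: 324 homes, 108 per area, and about 1.5 children per home (324 × 1.5 = 486 children).

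Assumed:

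- Household SD 0.7; within-area SD of ln PM2.5 0.8.
- In the order Montana/Navajo Nation/Alaska: AI/AN caregiver 8/95/95%, low income 30/60/50%, college 55/35/25%, smoker 15/15/40%.
- Ambient temperature −1/1/−8 °C with within-area SD 2 or 4; ambient PM2.5 geometric mean 8/6/6 (ln SD 0.5).
- The other covariates do not differ by area, and no covariate has its own effect on LRTI.

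Three cases of area PM2.5 geometric means and LRTI risks were each run in six area orderings. With V the variance of the three log means, the between-area share of ln PM2.5 variance is V/(V + 0.8²): 0.058/0.698 = 8% (mild), 0.171/0.811 = 21% (middle), 0.320/0.960 = 33% (strong).

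*No true effect: rejection at 5%, range over orderings.*

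| Case (PM2.5; risk %) | Household-only, SD 2 | Household-only, SD 4 | Spurious OR per 10 µg/m³ | Area intercept, SD 4 |
|---|---|---|---|---|
| Mild (15/20/27; 15/20/27) | 2–10% | 5–7% | 1.00–1.02 | 4–7% |
| Middle (12/20/33; 12/20/30) | 3–8% | 5–12% | 1.01–1.03 | 5–8% |
| Strong (10/20/40; 10/20/35) | 7–11% | 9–24% | 1.01–1.04 | 6–11% |

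With area fixed, rejection was 3–7% in all 3 × 6 × 2 = 36 settings, with OR 0.99–1.00. There was no inflation when areas did not differ (6%), differed only in PM2.5 (4%) or differed only in risk (3%). With 300 runs the Monte Carlo SE is √(0.05 × 0.95/300) = 1.3 points at 5%, and 2.5 points at 24%.

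*True OR 1.10 per 10 µg/m³, high-PM2.5 areas at low risk: mean power over orderings.*

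| Case | SD 2: household-only v area fixed | SD 4: household-only v area fixed | Area intercept, SD 4 |
|---|---|---|---|
| Mild | 51 v 57% | 51 v 61% | – |
| Middle | 49 v 64% | 38 v 63% | 53% |
| Strong | 43 v 69% | 32 v 69% | 59% |

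The median OR was 1.03–1.11 household-only, 1.09–1.11 with area fixed and 1.08–1.09 with an area intercept. The Monte Carlo SE of these mean powers is about 2 points. A repeat under the same assumptions gave similar results: null rejection up to 25%, OR up to 1.04, and strong-case power at SD 4 of about 36% v 75%.

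**The case against.** Area is in the model. The SAP's wording on clustering, and its separate mention of removing the household term, fit an expanded nesting with its own area intercept at least as well as a single factor. On that reading the simulated distortion is small. This stands: the material harm depends on the household-only reading, and the SAP does not say which was fitted. With only three areas, though, an area variance is poorly estimated, which favours a fixed term on either reading.

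The null-case bias is mostly small. This also stands. The mild case at SD 4 cannot be told apart from the area-fixed model. The 24% needs a fourfold PM2.5 gradient (40/10), a 3.5-fold risk gradient (35/10), an unfavourable ordering and SD 4 together. The power losses need high-PM2.5 areas to have low LRTI risk, which no part of the documents supports or rules out.

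The area profiles are invented. Because no covariate affects LRTI in the simulation, the whole area risk difference is residual by construction. In practice, whatever works through income, smoking or race would be adjusted away. This stands as a limit on size.

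Area may be among the unnamed additional ER confounders, or in the DAG, which is not available here. That cannot be told from the documents.

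The Alaska exclusion answers a difference in control treatment, which is a matter for the ITT comparisons. Its absence from ER is therefore not a gap in itself. None of these points supplies a stated fixed-area ER fit.

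**Conclusion.** The concern holds as a statement of possibility. A primary, non-randomised analysis omits study area from its fixed covariates, and no fixed-area check is stated for it. Confounding between areas needs area differences in both indoor PM2.5 and LRTI, and the documents give neither.

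Under the assumed differences and a household-only intercept, false-positive rates run from about nominal to 24%, with spurious ORs of at most 1.04 per 10 µg/m³. The larger risk is masking a real association, with mean power as low as 32% against 69%. With a separate area intercept both effects are small (rejection 4–11%; power 53–59% in the middle and strong cases). The randomised ITT comparisons are not affected. Confidence is medium, because the size rests on assumed values and on how the random term was coded.

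**What to change.** Report, beside the current ER model, a fit with study area (AK, NN, WMT) as a fixed factor plus a household random intercept, so that the PM2.5 coefficient is a within-area association. Printing the exact glmer random-effects formula of the current model would let readers judge how far the two should differ, but does not replace the added fit.

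The cost is one re-run and two degrees of freedom (3 − 1). Area will be partly collinear with caregiver race and ambient temperature, and the between-area PM2.5 contrast is no longer used. In the simulations, standard errors rose against the household-only model by 0–6% in the no-effect runs and 0–11% in the true-effect runs. No new data are needed: descriptive statistics were already produced "across all study households and separately for each treatment arm and study area", and area was already fitted as a fixed effect for ITT-LRTI. Agreement between the two ER fits would strengthen the result; if they differ, readers need to see it.
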